Fibromyalgia disease is characterized by a symptomatology that, in many cases, is diffuse and difficult to quantify. Among its most notable symptoms at the physiological level, both peripheral and central, the following should be highlighted. Lower strength production with risk of dynapenia, Latorre-Román, P. Á et al., (2015), low muscular endurance with possible alterations in muscle fiber typology Bonaterra, G. A et al., (2016), lower maximum oxygen consumption (VO_{2max}), with difficulties in obtaining the same due, in large part, to the problem of achieving maximum effort in this type of person, Valim, V et al., (2002); Bardal, E. M et al., (2013). This can be explained by a decrease in muscle performance due to pre-sarcopenia or even sarcopenia factors, which, due to the difficulty of a more invasive methodology in this type of people, its evaluation is greatly limited Koca, I et al., (2015). Likewise, it can be explained even, by an alteration in the kinetics on muscular VO_2 , Shang, Y et al., (2012), which further aggravates the generalized fatigue, since there is a low maximum aerobic power added to a poor utilization of the same at peripheral level, which translates into a limited cardiorespiratory and neuromuscular condition.

On the other hand, people diagnosed with fibromyalgia also have elevated oxidative stress levels with a decrease in antioxidants with respect to healthy people, Sarıfakioğlu, B et al., (2014). Which highlights a greater deterioration of neuromuscular functions, with a worse post-exertion recovery, being in this sense the aerobic and strength physical exercise fundamental to alleviate and modify this situation.

These circumstances result in a significant decrease in physical condition and, consequently, in the ability and personal autonomy of the patient in their daily routine, so it is of utmost importance to provide a response through an intervention work that can, both centrally and peripherally, achieve a significant improvement in the quality of life of these people.

On the other hand, several unlinked investigations on the role of the central nervous system (CNS) and nociceptive alterations, as, almost, the only explanation in the currentsCurrent studies on the diagnosis of fibromyalgia disease have shown that there is a mitochondrial alteration at various levels. These mitochondrial alterations include abnormal changes in their structure, a decrease in the number of mitochondria and an increase in their size in this type of person. Cordero, M. D et al., (2011); Sprott, H et al., (2004); Meeus, M et al., (2013), also, it has been found that people with fibromyalgia have lower values in the expression of PGC-1 α and Tfam and AMPK with respect to the

control group, Castro-Marrero, J et al., (2013), which may explain and shed light on the reason for many of the symptoms in people with fibromyalgia.

It is known that one of the causes for AMPK activation in conventional exercise and, more specifically, aerobic exercise, is an increase in the AMP-ATP ratio due to the very demands of the activity in terms of intensity and duration so, when at the cellular level they detect an energy imbalance AMPK is activated in the α catalytic domain by LKB1. In hypoxia it has been shown that it is also a trigger for the activation of this protein by LKB1, although the conditions that are met in conventional exercise are not the same as those that trigger this activation because in hypoxia the AMP-ATP ratio does not increase, but rather decreases. On the other hand, hypoxia also produced reactive oxygen species (ROS), postulating the research that, under hypoxia conditions AMPK activation is produced by oxidative stress and not by the AMP-ATP ratio. Emerling, B. M et al., (2009); Morales-Alamo, D et al., (2012).

In other research Hao, Z et al, (2015), where the role of hypoxia, blood flow deprivation and apoptosis in fracture healing, where hypoxia started shortly after the reduction of blood flow by the fracture itself, they proved that severe hypoxia is a limiting factor for fracture healing, but, on the other hand, they proved the role that hypoxia plays in the activation of AMPK, being this a protein activator, concluding that, hypoxia, ischemia and ROS potentially activate the AMPK signaling pathway, Laderoute, K. R et al, (2006).

Training by ischemic hypoxia is called occlusive, ischemic or Kaatsu training. It is a training technique that originated in Japan in the early 1980s and became popular in the late 1990s. This technique is based on the restriction or occlusion of blood flow during exercise, whether aerobic or strength exercise. This methodology was created in response to an aging Japanese population in order to alleviate falls and musculoskeletal disorders typical of age and thus provide an increase in the autonomy of the elderly population. This type of technique is developed as an alternative method to conventional strength training and aerobic exercise, where a physically limited population has a lower adherence at all levels, mainly due to the intensity and duration required to achieve significant physiological adaptations, so that the technique with occlusion makes sense because of achieving positive changes with a lower load to mobilize and less time to execute. On the other hand, the ischemia method is also very widespread in the field of sports performance, presumably due to the fact that the probability of injury decreases if a technique is used that provides the desired adaptations with a lower mobilization load and a more limited training duration, where several studies have shown its usefulness in terms of physiological improvements. Martín-Hernández, J et al., (2011).

These characteristics and previous research confirm the need to carry out research that continues to deepen the level of expression of mitochondrial proteins and their role in the quality of life and functional autonomy from the perspective of a physical intervention program adapted to the conditions mentioned above to carry out a structured and planned program in people with fibromyalgia.

Bibliographic references

- Latorre-Román, P. Á., Segura-Jiménez, V., Aparicio, V. A., e Campos, M. A. S., GarcíaPinillos, F., Herrador-Colmenero, M., & Delgado-Fernández, M. (2015). Ageing influence in the evolution of strength and muscle mass in women with fibromyalgia: the al-Ándalus project. *Rheumatology international*, 35(7), 1243-1250.
- Bonaterra, G. A., Then, H., Oezel, L., Schwarzbach, H., Ocker, M., Thieme, K., & Kinscherf, R. (2016). Morphological Alterations in Gastrocnemius and Soleus Muscles in Male and Female Mice in a Fibromyalgia Model. *PLoS one*,11(3), e0151116.

1- The training program has a positive impact on quality of life and functional autonomy in people with fibromyalgia.

2- The training program is effective and generates little fatigue.

3- The training program has a high adherence in people with fibromyalgia.

4- The hypoxia produced and the relative intensity of the program has a direct impact on the balance of oxidant/antioxidant levels.

5- The levels of TAS, MDA, liver enzymes, biochemical variables and hemogram remain stable without significant alterations.

6- Occlusive training in people with fibromyalgia proves to be an effective and safe therapy as part of the treatment.

Objectives

Main Objective

To improve the quality of life and functional autonomy.

Specific Objectives

- 1- To achieve results by minimizing the fatigue produced in people with fibromyalgia.

- 2- To get people accustomed to the adapted program and make it part of their routine.

- 3- To measure variables in blood/plasma to verify the results obtained for a better understanding of the disease and its impact.

- 4- To identify those blood/plasma variables most susceptible to occlusive training that will allow a better understanding of fibromyalgia disease.

- 5- To test the effectiveness and adherence of occlusive training in people with fibromyalgia by means of blood/plasma samples, functional tests and questionnaires.

- 6- To evaluate occlusive training as a valid physical complementary therapy for people with fibromyalgia.

Methodology

The methodology will be carried out by an experimental design research to test the effect of the independent variable on the dependent variable. In this case, the independent variable will be the pressure exerted by the occlusive cuff on the thigh musculature during the planning of aerobic exercise walking of low intensity and reduced time, and its impact on the dependent variable, which is determined by plasma and blood values, mitochondrial protein expression, standardized questionnaires of the impact of the disease (psychometric), and functional tests of physical condition (distances and times performed), which will be measured before and after the intervention period.

Study population

The study population will be men and women diagnosed with fibromyalgia between 18 and 70 years of age from Seville capital and province. In this way, a more representative sample will be included, since both active and sedentary people will be included. There will also be people who are active at work and people who are engaged in housework.

Sample size.

With a 95% CI and a percentage of 1.8% prevalence of the disease in Andalusia for both sexes, according to data collected from the Ministry of Health and Family in the year 2021 of people affected by fibromyalgia with a precision of $\pm 3\%$, the sample size is $n=75$.

Inclusion and exclusion criteria

Criteria for inclusion in the research

- A patient meets diagnostic criteria for fibromyalgia if the following three conditions are present: (American Rheumatology Association). Wolfe et al., (2010).
 - o 1) Widespread Pain Index (WPI) ≥ 7 and Symptom Severity Score (SS Score) ≥ 5 or WPI 3-6 and SS ≥ 9 .
- Symptoms have been present, at a similar level, during the last three months.
- The patient has no other pathology that could explain the pain.
- Recent negative COVID-19 test.

Exclusion criteria

- Other associated pathologies that may hinder the development of the investigation.
- Mobility limitations.
- Injuries that add to those of the disease itself and hinder mobility.
- No medical evaluation of the diagnosis of the disease.
- Negative results in the inclusion tests.
- Cardiac pathologies.
- Blood pressure higher than 130-90 mmHg.
- No COVID-19 test.

Definition of variables

-Independent variables:

- Cuff pressure to produce occlusion.
- Walking time and intensity.

Dependent variables:

- Psychometric questionnaires of impact of fibromyalgia disease:
- Symptom severity index (Score).
- Widespread Pain Index (WPI).
- Fibromyalgia Impact Questionnaire (FIQ).
- Multidimensional Fatigue Inventory (MFI-20).
- Blood/plasma measurements.
- Biochemical values.
- Oxidative stress, total antioxidants and Coenzyme-Q values.
- Standardized physical fitness tests
 - Time up and Go test.
 - 30-second chair stand test (Cycles).
 - 6-minute walk test (distance covered).
 - Lower body dynamometer test (Newtons of force).
 - Hand press test (Newtons of force).

Data collection

Data collection will be based mainly on 3 stages.

Stage 1

Once the screening on inclusion and exclusion sections has been passed and carried out, the following should be done:

1. Standardized disease questionnaires.

- WPI
- SScore
- FIQ
- MFI-20

2. Blood draw by nursing team at Santa Ángela de la Cruz Viamed Hospital (Seville).

3. Standardized physical tests to determine baseline physical condition (collection of field work data on a sheet for this purpose).

- Time up and Go test.
- 30-second chair stand test.
- 6-minute walk test.
- Dynamometer test with lower body dynamometer.
- Hand press test.

Stage 2

In this stage the intervention period of 10 weeks will be carried out 2 days per week with a total of 20 sessions and with a duration per session of 20 minutes of occlusive aerobic training. The data collected will be carried out with a daily record sheet for each of the participants.

Stage 3

Once the intervention period is over, all the tests that were carried out in stage 1 will be retaken.

4. Standardized disease questionnaires.

- WPI
- SScore
- FIQ
- MFI-20

5. Blood draw by nursing team at Santa Ángela de la Cruz Viamed Hospital (Seville).

6. Standardized physical tests to determine baseline physical condition (collection of field work data on a sheet for this purpose).

- Time up and Go test.
- 30-second chair stand test.
- 6-minute walk test.
- Dynamometer test with lower body dynamometer.
- Hand press test.

Statistical analysis

Descriptive statistics were calculated for each variable. The normality of the distribution of data was verified by the Shapiro-Wilk test. Variables showing skewed distributions were log-transformed to obtain a normal distribution. Relative changes within each group were assessed using a paired Student's t test. To compare baseline variables the Student's t test, standardized differences ($\pm 90\%$ confidence level) and qualitative differences were estimated. To detect between-group differences, multiple 2 x 2 (group x time) mixed-analysis of variance was performed and adjustments for multiple comparisons were made using the Bonferroni method by dividing the significance level of 0.050 by the number of comparisons, additionally standardized differences ($\pm 90\%$ CL) and qualitative differences were estimated. The effect size of standardized differences was determined by Cohen's d statistic, and the Hopkins' scale was used to determine the magnitude of the effect size, where 0 to 0.19 = trivial, 0.20 to 0.59 = small, 0.60 to 1.19 = moderate, 1.2 to 1.99 = large, and >2 = very large (Hopkins et al 2009). A practically worthwhile difference was assumed when the difference score was ≥ 0.2 of the between-subject SD. Qualitative assessment indicates the likelihood for the between-group differences to be substantial, referring to possible differences, to likely, to very likely, and to almost certain differences. The probability of a true difference between groups was qualitatively classified as almost certainly not: $<0.5\%$; very unlikely: 0.5% to 5%; unlikely: 5% to 25%; possible: 25% to 75%; likely: 75% to 95%; very likely: 95% to 99.5%; and almost certain: $>99.5\%$. A substantial effect was defined as $>75\%$ (Batterham and Hopkins 2006).

Functional tests

30-second chair stand test

Objectives: (Test No. 1)

1-To assess the strength of the extensor muscles of the knees and hips, responsible for gait failure and falls in 30 seconds.

2-To evaluate the resistance to loss of lower body strength, which causes early fatigue, in 30 seconds.

3- To evaluate the perceived effort and relative intensity of the patient's effort.

Bibliographic references. Validity and standardization


Test measurements (variables).

- Cycles performed will be counted
- Modified Borg Perceived Exertion Scale (1-10)
- Pulse oximeter (saturation and heart rate before and after)

Transfer of the test to the intervention period

This test will indicate whether after the training intervention period the patient has increased resistance to loss of lower body strength, with an increase in the number of cycles (standing and sitting) and a lower relative intensity of perceived exertion.

<https://upotv.upo.es/video/58da21db238583e0478b48f3>

Time and Go test

Objectives: (Test nº 2)

1- To evaluate agility, coordination and dynamic balance.

Bibliographical references. Validity and standardization

Test measurements (variables).

- The time it takes to stand up, walk a given distance, and sit down again will be counted.
- Modified Borg Perceived Exertion Scale (1-10)

Transfer of the test to the intervention period

This test will indicate whether coordination, balance and agility have improved after the intervention period due to an improvement in the muscular response of the lower body, having a direct transfer to avoid possible falls and stumbles.

<https://www.youtube.com/watch?v=8eRQexJzzUE>

6-minute walk test

Objectives: (Test nº 3)

- 1-To evaluate the resistance to the loss of lower body strength that causes early fatigue.
- 2- To evaluate the aerobic endurance capacity through its physical and physiological condition.
- 3- To evaluate the perceived effort and relative intensity of the patient's effort.
- 4-To indirectly evaluate their Vo2max.

Bibliographic references. Validity and standardization

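### Hypothesis 5 claims stable blood values, but no decision rule is assigned to it, and non-significance in 7 v 6 people cannot show stability

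*Combined protocol and SAP*

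**What the plan says.** Hypothesis 5 predicts that "The levels of TAS, MDA, liver enzymes, biochemical variables and hemogram remain stable without significant alterations". It gives no margin, reference range or permitted change, and does not say whether stability is judged over time within the cuff group or between the groups.

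The Statistical analysis section provides:

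- a within-group difference test: "Relative changes within each group were assessed using a paired" t test;
- a 2 x 2 group-by-time mixed ANOVA between groups, where "adjustments for multiple comparisons were made using the Bonferroni method by dividing the significance level of 0.050 by the number of comparisons" (the number of comparisons is not given);
- standardized between-group differences with 90% limits;
- a threshold: "A practically worthwhile difference was assumed when the difference score was ≥ 0.2 of the between-subject SD";
- a likelihood scale: "Qualitative assessment indicates the likelihood for the between-group differences to be substantial". It has low bands (unlikely, very unlikely, almost certainly not), but the only cut-off used for a decision is above 75%, for a substantial effect.

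None of these is tied to Hypothesis 5. Participants' arms reports 7 people with the cuff and 6 without.

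Two neighbouring hypotheses matter. Hypothesis 4 reads "The hypoxia produced and the relative intensity of the program has a direct impact on the balance of oxidant/antioxidant levels", with no marker or direction. Hypothesis 6 reads "Occlusive training in people with fibromyalgia proves to be an effective and safe therapy as part of the treatment". Definition of variables lists "Oxidative stress, total antioxidants and Coenzyme-Q values" among the outcomes.

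**The concern.** A claim of no change needs evidence that any change is small. A test that seeks a difference gives that evidence only if it would have detected the changes that matter. Read statistically, Hypothesis 5 is confirmed when the tests find nothing, so a small sample and a Bonferroni correction both make it easier to confirm. The risk is that blood values are reported as stable because 13 people were too few to show movement.

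A secondary wording point concerns Hypotheses 4 and 5. If TAS and MDA are the antioxidant and oxidant measures (an assumption, since the document expands neither), both hypotheses may cover them. A change could then be counted for Hypothesis 4 and no change for Hypothesis 5.

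**Working it through.** **The plan's own figure.** The only computed number is the sample size: 1.96² × 0.018 × 0.982 / 0.03² = 75.4, which reproduces 75. It is a precision calculation for a prevalence and gives no power for Hypothesis 5.

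**Inputs.** From the documents: n = 7 and 6; significance level 0.05; 0.2 between-subject SD as the worthwhile difference. Assumed: two-sided tests, and a pre-post correlation r of 0.5, 0.7 or 0.9 (none is given).

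**Formulas, in units of the between-subject SD.**

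- SD of change = √(2(1 − r)) = 1.000 / 0.775 / 0.447.
- SE within the 7 = SD of change / √7 = 0.378 / 0.293 / 0.169, with 6 df.
- SE for 7 v 6 = SD of change × √(1/7 + 1/6) = SD of change × 0.556 = 0.556 / 0.431 / 0.249, with 11 df. This t test on change scores is the group-by-time test.
- Chance of missing a true change δ = probability that a noncentral t with noncentrality δ/SE lies within ± the critical value (2.447 for 6 df, 2.201 for 11 df).

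**Chance that a true change is non-significant (r = 0.5 / 0.7 / 0.9).**

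| True change | Paired, n = 7 | 7 v 6 |
|---|---|---|
| 0.2 SD | 93% / 91% / 83% | 94% / 93% / 89% |
| 0.5 SD | 80% / 70% / 31% | 87% / 81% / 55% |
| 1.0 SD | 40% / 19% / 0.2% | 62% / 44% / 5% |

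**Bonferroni.** With an assumed 5 comparisons (level 0.05/5 = 0.01), the 7 v 6 miss rate at 0.5 SD rises from 87% / 81% / 55% to 96% / 94% / 80%.

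**Could the existing threshold and scale be used instead?** Suppose the observed 7 v 6 difference is exactly zero. Using a t distribution with 11 df and the SEs above (flat prior), the probability that the true difference lies within 0.2 SD is 27% / 35% / 56%. That most favourable result still leaves stability within 0.2 SD unproven.

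**What intervals would show.** The 90% half-width is 1.943 × SE within the 7 = 0.73 / 0.57 / 0.33 SD, and 1.796 × SE for 7 v 6 = 1.00 / 0.77 / 0.45 SD. The chance of placing the 90% interval inside a margin when there is no true change is:

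| Margin | Within the 7 | 7 v 6 |
|---|---|---|
| 0.2 SD | under 2% at every r | about 0% at every r |
| 0.5 SD | 3% / 11% / 67% | 0.05% / 0.5% / 23.5% |
| 0.8 SD | 27% / 57% / 99% | 3% / 16% / 83% |

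**The case against.** Four objections deserve an answer.

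1. *The plan does have tools.* A reader might infer that nothing in it bears on stability. That goes too far. The 0.2 SD threshold, the low-likelihood bands and the between-group 90% limits are close to what is needed. What is missing is a cut-off assigned to Hypothesis 5.

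2. *The miss rates depend on the size of change.* A reader might infer that the study would overlook almost any change. The table does not support that. The rates of 83% to 94% hold only at 0.2 SD, which the plan calls practically worthwhile and not a safety limit. Change over time is the more natural reading of stable, and there a 1.0 SD change is missed between 0.2% and 40% of the time, depending almost wholly on the assumed r.

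3. *The word significant may be clinical.* If so, none of the power figures applies. The remaining gap is that no reference range is stated.

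4. *The links to Hypotheses 4 and 6 are conditional.* A reader might infer that the safety claim in Hypothesis 6 rests on Hypothesis 5. No section says so, and saturation, heart rate and pain are also recorded at each session. A reader might also see a flat contradiction between Hypotheses 4 and 5. But one concerns a balance and the other levels, and the overlap depends on what TAS and MDA stand for.

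All four stand as limits on the point. None supplies a rule for calling a value stable.

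**Conclusion.** The concern holds in limited form, and the point should be fixed. Hypothesis 5 has no criterion, and on the statistical reading the planned tests would let non-significance in 7 v 6 people pass as stability. For changes near the plan's own 0.2 SD threshold, non-significance is the usual result whether or not the values moved. At 0.5 SD the miss rate is 31% to 80% within the cuff group and 55% to 87% between groups. Large changes would often be seen within the cuff group if r is high.

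The figures rest on two-sided tests, r between 0.5 and 0.9, and the reported group sizes. The conclusion concerns blood values and not the main objective of quality of life and functional autonomy. The links to Hypotheses 4 and 6 are wording points and do not carry it.

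**What to change.** 1. Do not report non-significance as stability. For each analyte under Hypothesis 5, use the between-group 90% limits already planned and add a 90% confidence interval for the change within the cuff group. Call the analyte stable only if the interval lies inside a margin fixed before results are seen (a ratio if the analyte is log-transformed); otherwise call it inconclusive. State which comparison decides.
2. If results have already been seen (Statistical analysis and Participants' arms are partly in the past tense), report the intervals only and label Hypothesis 5 exploratory.
3. If the clinical meaning was intended, say so and state the laboratory reference range used.
4. State that any laboratory part of the safety claim in Hypothesis 6 does not rest on non-significant tests.
5. Have the investigators reconcile Hypotheses 4 and 5 by naming the markers and the expected direction for each.

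The cost is wording plus one margin per analyte. The biochemistry and hemogram panels are not itemised, so the number of margins is unknown. No new data are needed. The downside is that most analytes will probably be inconclusive, because the 90% half-width is 0.33 to 0.73 SD within the 7 and 0.45 to 1.00 SD between groups. That is an accurate account of what 13 people can show.

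### Blood safety is tested only on group means, with no criterion for an individual result; at n = 7 one isolated marked rise gives a paired t near 1, so non-significance cannot support stability or safety

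*Combined protocol and SAP*

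**What the plan says.** In the Hypothesis section of the combined protocol and SAP, hypothesis 5 reads: "The levels of TAS, MDA, liver enzymes, biochemical variables and hemogram remain stable without significant alterations". Hypothesis 6 is that occlusive training "proves to be an effective and safe therapy as part of the treatment". The documents do not say whether significant in hypothesis 5 means statistically or clinically significant, and they give no margin.

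Blood is drawn once before the intervention (Week 1) and once after it (Week 13), according to Data collection and Timing of phases and weeks.

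The Statistical analysis section is the only analysis text, and it has no separate safety part. It begins: "Descriptive statistics were calculated for each variable". For change within an arm: "Relative changes within each group were assessed using a paired Student's t test". For arm differences, "multiple 2 x 2 (group x time) mixed-analysis of variance was performed", with a Bonferroni correction "by dividing the significance level of 0.050 by the number of comparisons". It adds standardized differences with 90% limits. A difference of at least "0.2 of the between-subject SD" counts as worthwhile, and a probability above 75% on the qualitative scale counts as substantial.

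The arms are 7 participants with the cuff and 6 without (Participants' arms).

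**The concern.** An abnormal liver enzyme or blood count occurs in a person. The plan asks whether the mean moved. A single extreme value moves the mean a little, but it also inflates the standard deviation by which the mean change is judged, and in a group of seven the two effects nearly cancel.

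This is not ordinary low power. Power normally rises with the size of the effect; here a larger isolated abnormality makes a significant result less likely. Nor would a margin on the mean cure it, because a mean margin does not show who became abnormal or how many did.

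At stake is the safety conclusion. The plan as written could report the bloods as stable and the therapy as safe while one of seven cuff participants had a grossly abnormal result.

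**Working it through.** **The plan's own figure.** The only sample-size calculation is for a prevalence: 1.96² × 0.018 × 0.982 / 0.03² = 75.4, which reproduces the stated 75. It has no bearing on blood safety, and the arms described hold 13 participants.

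**Inputs.** Arm sizes 7 and 6, the paired t test, the 2 x 2 mixed ANOVA and alpha 0.05 come from the documents. Assumed here: two-sided tests, complete pairs, and no Bonferroni divisor, since the number of comparisons is not given (any divisor above 1 makes detection harder).

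**One riser, the others unchanged.** The changes are D, 0, ..., 0.
- Mean = D/n; SD = D/√n; SE = SD/√n = D/n; so t = 1 for any D.
- n = 7: 6 df, p = 0.356 (critical t 2.447). n = 6: 5 df, p = 0.363.
- The planned log transformation does not help. The log changes are again one non-zero value and zeros, so t = 1.

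**Group x time, one riser in the cuff arm.** The interaction F is the square of the two-sample t on the change scores.
- Mean difference = D/7 = 0.1429D.
- Pooled SD = D√((6/7)/11) = 0.2791D.
- SE = 0.2791D × √(1/7 + 1/6) = 0.1553D.
- t = 0.1429/0.1553 = 0.92, 11 df, p = 0.377.

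**Several equal risers among seven.** t = √(k(n−1)/(n−k)).
- k = 2: √(12/5) = 1.55, p = 0.172.
- k = 3: √(18/4) = 2.12, p = 0.078.
- k = 4: √(24/3) = 2.83, p = 0.030.

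On this pattern, four of seven must rise before the paired test reaches 0.05.

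**With variation in the others.** Simulation, 100,000 runs per setting, n = 7. Changes are normal with mean 0 and SD 1 (an assumption; only the ratio of rise to SD matters), and one participant has an extra rise.

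| Extra rise (SD of change) | Median t | P(p < 0.05) |
|---|---|---|
| 0 | 0.00 | 5.0% |
| 2 | 0.63 | 4.3% |
| 3 | 0.77 | 3.2% |
| 5 | 0.90 | 0.8% |
| 10 | 0.97 | <0.01% |

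**When everyone also shifts by 1 SD.** With no extra rise the test is significant in 60% of runs. With an extra 3 SD in one participant, median t is 2.58 and 56% are significant; with an extra 10 SD, 1.65 and 1.4%; with an extra 50 SD, median t is 1.14. The significance here comes mainly from the common shift, and a large individual rise removes it.

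**Qualitative scale.** This is P(difference > 0.2 SD) from a t distribution with 11 df, for 7 v 6 with the other 12 participants unchanged. With the baseline SD as yardstick it is 0.68 at 3 SD, 0.74 at 5 SD, 0.78 at 10 SD and 0.81 in the limit. If the yardstick SD includes the outlier, the limit is P(t < (0.1429 − 0.2 × 0.2791)/0.1553) = P(t < 0.56) = 0.71.

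**What an empty count shows.** The exact two-sided 95% upper limit for 0 of 7 is 1 − 0.025^(1/7) = 0.41; for 0 of 6 it is 1 − 0.025^(1/6) = 0.46.

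**The case against.** A reader might infer that blood safety rests on t tests alone, that t is about 1 however large the rise, and that individual harm can never show. The documents and the figures do not support any of these in full.

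- **Other tools are planned.** The section also has descriptive statistics, a mixed ANOVA, standardized differences and a probability scale. With the baseline SD as yardstick, one very large rise passes the 75% rule; with an SD that includes the outlier it does not. The section does not say which SD applies. This rules out the word never, but a substantial label would still describe a mean difference and would not identify the participant. Descriptive statistics could expose an outlier if ranges were reported, but the section does not say that they will be.
- **t = 1 is exact only if nobody else changes.** Otherwise it is the limit for a very large isolated rise. Moderate isolated rises are significant in about 3 to 4% of runs, and t can be well above 1 when the others shift too.
- **Significant may mean clinically significant.** In that case the t test would not be the criterion for hypothesis 5. The documents leave this open, so the statistical reading is an inference. They offer no other criterion.
- **Individual safety data are collected.** Oxygen saturation, heart rate and pain are recorded for each participant at every session, so hypothesis 6 does not rest on bloods alone. These records do not cover liver enzymes, biochemistry or haemogram.

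These points narrow the claim. None of them supplies an individual-level analysis of the bloods.

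**Conclusion.** The point holds in this form: all planned inference on liver enzymes, biochemistry and haemogram concerns group means, no individual criterion is stated, and at n = 7 an isolated marked rise drives the paired t towards 1. The size is p = 0.356 within the cuff arm and p = 0.377 for group x time if the others do not change. With normal variation around zero change in the others, the chance of p < 0.05 falls to about 3% at 3 SD and under 1% at 5 SD, below the test's own 5% error rate. A non-significant mean change is therefore no support for hypothesis 5, read statistically, or for the laboratory part of hypothesis 6.

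The closed-form results need only the stated arm sizes, two-sided tests and complete pairs. The simulated percentages also rest on the assumed normal changes with mean zero. The change should be made, but the plan should not be described as unable ever to reveal individual harm.

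**What to change.** For liver enzymes, biochemistry and haemogram, amend the Statistical analysis section so that hypothesis 5 and the laboratory part of hypothesis 6 rest on:

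1. a listing of each participant's Week 1 and Week 13 values against the laboratory's reference range;
2. a shift table by arm, counting for each analyte the results newly outside the range, with exact two-sided 95% limits.

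Keep mean changes as description, and state that a non-significant mean change will not be taken as evidence of stability. If the 75% scale is kept, name the SD that it uses.

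The data are already collected, so the cost is SAP wording, one listing of 13 participants and one table. No extra visit, participant or clinical rule is involved. The downside is a more cautious conclusion: even no new abnormality among seven cuff participants leaves a true rate of up to 41% compatible with the data, and the safety statement has to say so.
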